13.4 Clinical Follow-up

Patients achieving CR90, PR, or SD, and who have completed 24 months of treatment will be observed for clinical follow-up at 30 and 90 days after the end of treatment, and then proceed to survival follow-up.

13.5 Duration of therapy for CR

The maximum duration of therapy is 24 months. Patients who achieve CR during this period will be removed from active treatment and will proceed to survival follow-up, thus duration of therapy for CR will be 24 months or less.

13.6 Duration of therapy for CR90, PR or SD

Patients who achieve CR90, PR, or SD will continue on therapy up to a maximum duration of 24 months.. After 24 months,, the patients will continue to clinical follow-up at 30 and 90 days after the last treatment and then proceed to survival follow-up (see 13.4 above). Subsequent treatment is at the discretion of their attending.

13.7 Ineligible

A patient is deemed *ineligible* if after registration, it is determined that at the time of registration, the patient did not satisfy each and every eligibility criteria for study entry. If the patient received treatment, the patient may continue treatment at the discretion of the physician as long as there are not safety concerns. The patient will continue in the Active Monitoring/Treatment phase of the study, as per section 4.0 of the protocol.

- If the patient never received treatment, on-study material must be submitted. Survival Follow-up will be required per Section 4.0 of the protocol.

13.8 Major violation

A patient is deemed a *major violation*, if protocol requirements regarding treatment in cycle 1 of the initial therapy are severely violated that evalability for primary end point is questionable. If the patient received treatment, the patient may continue treatment at the discretion of the physician as long as there are no safety concerns. The patient will continue in the Active Monitoring/Treatment phase of the study, as per section 4.0 of the protocol.

13.9 Cancel

A patient is deemed a *cancel* if he/she is removed from the study for any reason before any study treatment is given. On-study material and the End of Active Treatment/Cancel Notification Form must be submitted. No further data submission is necessary.

14.0 Body Fluid Biospecimens

None.

15.0 Drug Information

IND number (139381)

- Investigator brochure

Industry-supplied:

(drug company contact: : [REDACTED]
[REDACTED]

15.1 Pembrolizumab (MK-3475, SCH 900475, Keytruda®)

15.11 Background: Pembrolizumab is a potent humanized IgG4 monoclonal antibody with high specificity of binding to the PD-1 receptor, thus inhibiting its interaction with PD-L1 and PD-L2. Based on preclinical *in vitro* data, pembrolizumab has high affinity and potent receptor blocking activity for PD-1.

15.12 Formulation:

Pembrolizumab is available as a liquid 25 mg/mL, 100 mg/vial.

15.13 Preparation and storage:

Vials should be stored in the refrigerator at temperatures between 2-8°C.

Drug concentrate is further diluted with normal saline (or 5% dextrose) in the concentration range of 1 to 10 mg/mL. The infusion solution in the IV bag should be immediately administered. Diluted pembrolizumab solutions may be stored at room temperature for a cumulative period of up to 46 hours. This includes room temperature storage of admixture solutions in the IV bags and the duration of infusion. The product can also be stored under refrigeration at 2°C to 8°C for no more than 96 hours from the time of dilution. If refrigerated, the diluted solution must be allowed to come to room temperature prior to administration. The solution must be discarded after 6 hours at room temperature or 96 hours under refrigeration.

15.14 Administration: Pembrolizumab is administered by intravenous infusion over 30 minutes via a 0.22 micron in-line filter. The final infusion volume must be between 1 and 10 mg/mL. Maximum rate of infusion should not exceed 6.7 mL/minute through a peripheral or indwelling catheter. Flush the line with 0.9% NaCL following the completion of the infusion.

15.15 Pharmacokinetic information:

- a) Absorption –Because pembrolizumab is administered intravenously, it is immediately and completely bioavailable. Steady-state concentrations of pembrolizumab are reached by 16 weeks of repeated dosing with a Q3W regimen and the systemic accumulation is 2.1-fold. The peak concentration, trough concentration, and area under the plasma concentration versus time curve at steady state of pembrolizumab increased dose proportionally in the dose range of 2 to 10 mg/kg Q3W.
- b) Distribution – Pembrolizumab has a limited volume of distribution.

- c) Excretion – CL is approximately 23% lower after achieving maximal change at steady state compared with the first dose. The terminal elimination half-life ($t_{1/2}$) is estimated to be 22 days at steady state.
- d) Metabolism - Pembrolizumab is catabolized through non-specific pathways; metabolism does not contribute to its CL.

There are limited clinical studies on the subcutaneous formulation. Model-based analysis showed an estimated bioavailability of 64% (95% CI: 54% to 74%; variability, 128% CV). This is consistent with the reported bioavailability for other mAbs (range: 50% to 85%) given SC. Clearance was the same for the IV and SC formulations. The mean time to achieve maximum concentration (Tmax) with pembrolizumab SC was estimated to be 5.5 days (range: 3 days to 14 days).

15.16 Potential Drug Interactions: There are no known significant drug interactions.

15.17 Known potential adverse events:

Very common known potential toxicities, $\geq 10\%$:

Gastrointestinal disorders: diarrhea, nausea

Cardiovascular: cardiac arrhythmia, peripheral edema

Dermatologic: pruritis, skin rash, vitiligo

Endocrine and metabolic: decreased serum bicarbonate, hypercalcemia, hypercholesterolemia, hyperglycemia, hyperkalemia, hypertriglyceridemia, hypoalbuminemia, hypocalcemia, hypoglycemia, hypokalemia, hypomagnesemia, hyponatremia, hypophosphatemia, hypothyroidism, weight loss, constipation, decreased appetite, vomiting

Genitourinary: hematuria, urinary tract infection

Hematologic and oncologic: anemia, hemorrhage, increased INR, leukopenia, lymphocytopenia, neutropenia, prolonged partial thromboplastin time, thrombocytopenia Hepatic: hyperbilirubinemia, increased serum alanine aminotransferase, increased serum alkaline phosphatase, increased serum aspartate aminotransferase

Infection: infection

Nervous system: fatigue, headache, pain, peripheral neuropathy

Neuromuscular & skeletal: arthralgia, asthenia, back pain, musculoskeletal pain, myalgia

Renal: increased serum creatinine

Respiratory: cough, dyspnea, flu-like symptoms, pneumonia, pneumonitis, upper respiratory tract infection

Miscellaneous: fever

Common known potential adverse events, $\geq 1\% \text{ to } < 10\%$

Cardiovascular: acute myocardial infarction, cardiac tamponade, facial edema, ischemic heart disease, myocarditis, pericardial effusion, pericarditis, pulmonary embolism

Endocrine & metabolic: hyperthyroidism, thyroiditis

Gastrointestinal: colitis, dysphagia, stomatitis

Hematologic & oncologic: febrile neutropenia, tumor flare

Hepatic: ascites, hepatitis
Immunologic: antibody development
Infection: herpes virus infection, herpes zoster infection, sepsis
Nervous system: altered mental status, confusion, dizziness, insomnia
Neuromuscular & skeletal: arthritis, myositis, neck pain
Ophthalmic: uveitis
Renal: acute kidney injury
Respiratory: nasopharyngitis, oropharyngeal pain, pleural effusion, respiratory

failure

Miscellaneous: fistula, infusion related reaction

Uncommon known potential adverse events , $\geq 0.1\%$ to $<1\%$:

Cardiovascular: Vasculitis

Endocrine & metabolic: adrenocortical insufficiency, diabetic ketoacidosis, hypoparathyroidism, hypophysitis, type 1 diabetes mellitus

Gastrointestinal: duodenitis, gastritis, increased serum amylase, increased serum lipase, pancreatitis

Hematologic & oncologic: aplastic anemia, hemolytic anemia, immune thrombocytopenia, immunological signs and symptoms (hemophagocytic lymphohistiocytosis), lymphadenitis (histiocytic necrotizing lymphadenitis [Kikuchi lymphadenitis]), sarcoidosis

Hypersensitivity: anaphylaxis

Immunologic: organ transplant rejection (solid)

Infection: Systemic inflammatory response syndrome

Nervous system: demyelinating disease, encephalitis, exacerbation of myasthenia gravis, Guillain-Barre syndrome, meningitis, myasthenia (myasthenic syndrome), myasthenia gravis, neuropathy (autoimmune), paresis (nerve)

Neuromuscular & skeletal: myelitis, polymyalgia rheumatica, polymyositis, rhabdomyolysis

Ophthalmic: iritis

Renal: nephritis

The risk profile for pembrolizumab also includes two important potential risks: a) myasthenic syndrome, and b) an increased risk of severe complications (such as early severe graft versus host disease and veno-occlusive disease) of allogeneic transplant in patients with hematologic malignancies who have previously been treated with PD-1 inhibitors.

Since the last IB, Edition 21, a new identified risk of hypoparathyroidism has been added to the warnings and precautions section of the CCDS based on routine pharmacovigilance.

Per IB, Edition 23 a new risk of optic neuritis has been added to the Postmarketing Experience Adverse Reactions section of the CCDS based on routine pharmacovigilance.

Patients with multiple myeloma who were treated with pembrolizumab in combination with either pomalidomide or lenalidomide and dexamethasone, had an increased number of serious side effects and deaths as compared to patients who received only dexamethasone and either pomalidomide or lenalidomide. The benefit-risk profile is unfavorable for the combination of pembrolizumab, pomalidomide, and dexamethasone in relapsed refractory multiple myeloma, and the combination of pembrolizumab, lenalidomide, and dexamethasone in newly diagnosed treatment-naïve multiple myeloma.

Post marketing reports have identified additional adverse reactions, including arthritis, Vogt-Koyanagi-Harada syndrome and hemophagocytic lymphohistiocytosis. Because these reactions are reported voluntarily from a population of uncertain size, it is not always possible to reliably estimate their frequency or establish a causal relationship to drug exposure.

15.18 Drug procurement:

Pembrolizumab will be provided free of charge to study participants by Merck.

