7.0 Protocol Treatment

7.1 Treatment Schedule

Agent	Dose	Route	Day	Cycles
Pembrolizumab	200 mg	IV	Day 1	q3 weeks until disease progression, intolerable toxicity, or CR for a maximum duration of 24 months

Protocol treatment should be administered on Day 1 of each cycle after all procedures/assessments have been completed as detailed on the Test Schedule (Section 4.0). Trial treatment may be administered up to 3 days before or after the scheduled Day 1 of each cycle due to administrative reasons.

All trial treatments will be administered on an outpatient basis.

Pembrolizumab 200 mg will be administered as a 30 minute IV infusion every 3 weeks. Sites should make every effort to target infusion timing to be as close to 30 minutes as possible. However, given the variability of infusion pumps from site to site, a window of -5 minutes and +10 minutes is permitted (i.e., infusion time is 30 minutes: -5 min/+10 min).

The Pharmacy Manual contains specific instructions for the preparation of the pembrolizumab infusion fluid and administration of infusion solution.

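### Section 15.13 gives two room-temperature limits for diluted pembrolizumab, 46 hours and 6 hours; the 46-hour figure is the one out of line

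*Combined protocol and SAP*

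**What the plan says.** Section 15.13 (Preparation and storage) of the combined protocol and SAP covers the diluted drug in one paragraph. In the order of the text:

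- Default handling: "The infusion solution in the IV bag should be immediately administered".
- Room-temperature allowance: "Diluted pembrolizumab solutions may be stored at room temperature for a cumulative period of up to 46 hours".
- What that time covers: "This includes room temperature storage of admixture solutions in the IV bags and the duration of infusion".
- Refrigerated allowance, at 2 to 8 °C: "for no more than 96 hours from the time of dilution". A refrigerated bag must then warm to room temperature before use.
- Discard rule: "The solution must be discarded after 6 hours at room temperature or 96 hours under refrigeration".

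Section 7.1 sets a 30-minute infusion, for which "a window of -5 minutes and +10 minutes is permitted", and places all treatment in the outpatient setting. It also points to a further source: "The Pharmacy Manual contains specific instructions for the preparation of the pembrolizumab infusion fluid and administration of infusion solution". That manual is not part of the documents reviewed here.

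**The concern.** The allowance and the discard rule give different limits for the same product in the same state. Staff who stop at the allowance could give a patient a bag that the protocol itself says should already have been discarded. For an infused drug, the storage limit is an operative instruction and not background text, so it should have one value.

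There is a smaller drafting problem as well. Only the 46-hour sentence and the one after it say that room-temperature time is cumulative and includes the infusion. The 6-hour sentence does not. A reader who sets the 46-hour sentence aside as wrong may lose the counting rule with it.

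**Working it through.** The plan derives no figure here, so there is nothing to reproduce. The check is a comparison of the sentences, with a little arithmetic to size the gap.

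**Inputs**

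| Item | Where stated | Room temperature | Refrigerated |
|---|---|---|---|
| Storage allowance | 15.13, middle of paragraph | 46 h, cumulative, infusion included | 96 h from dilution |
| Discard rule | 15.13, last sentence | 6 h | 96 h |
| Infusion time | 7.1 | 30 min, −5/+10 min | not applicable |

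The refrigerated limits agree. The room-temperature limits do not.

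**Can both figures be right?** Three readings would reconcile them, and none fits the text.

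1. *The 46 hours is a total that includes refrigeration.* The sentence is limited to room temperature, and refrigeration is introduced afterwards as a separate option. A 46-hour total would also contradict the 96 hours allowed in the refrigerator.
2. *The 6 hours applies only after a bag leaves the refrigerator.* The discard sentence lists room temperature and refrigeration as alternatives and does not depend on earlier refrigeration.
3. *One figure is for vials, the other for the diluted solution.* The 46-hour sentence names diluted solution. The discard sentence directly follows a sentence about the diluted solution, and its 96 hours is the limit counted from dilution.

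**Size of the conflict.** Let T be cumulative time at room temperature.

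- T ≤ 6 h: both sentences allow use.
- 6 h < T ≤ 46 h: one allows use, the other requires discard.
- T > 46 h: neither allows use.

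The conflicting band is 46 − 6 = 40 h wide, and 46 / 6 = 7.7. These numbers measure the difference in the text. They do not estimate exposure or harm.

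**Which figure is out of line?** Putting 6 in both places, or 46 in both places, would make the paragraph agree with itself, so consistency alone does not decide. The following points favour 6:

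- The 6-hour sentence is an obligation (*must*); the 46-hour sentence is a permission (*may*).
- The discard sentence restates the refrigerated limit correctly, so it reads as a summary of the storage limits.
- The default is immediate use, which fits a short holding time far better than almost two days.
- Nothing else in the documents supports 46 hours.

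**Is 6 hours workable?** Six hours is 6 × 60 = 360 min. If it includes the infusion, the time left for preparation, warming and holding is:

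- longest permitted infusion, 30 + 10 = 40 min: 360 − 40 = 320 min (5 h 20 min);
- nominal infusion, 30 min: 360 − 30 = 330 min (5 h 30 min).

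That is ample for outpatient dosing.

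**The case against.** The strongest objection concerns where the 46 comes from. If an edit replaced a 4 with a 6 and the deleted digit remained as strikethrough, the text form of the document would show 46 although the page a pharmacist sees would not. Stray double punctuation in Sections 13.1, 13.6 and 17.31 shows that the document was edited without a final clean-up. This fits a struck-through digit, but it fits equally well an editing slip that is visible on the page. The text cannot settle it. If the page does show a strikethrough, there is no contradiction to correct.

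The second objection is that the paragraph already contains a safe rule. Discarding at 6 hours breaches none of its sentences, so harm requires staff to act on a permission and overlook an obligation four sentences later. This stands, and it limits the importance of the point.

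Third, pharmacy staff may work from the Pharmacy Manual and never use the 46-hour figure. That is possible but cannot be checked here, and a correct manual would still leave a conflicting figure in the protocol.

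Fourth, the reach is small: treatment must start at one site (Section 6.5), and accrual stops at 10 patients under Amendment 4 (Section 16.31). This also stands.

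These objections cap the severity and make a check the first step. None of them reconciles the two sentences as written.

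**Conclusion.** The concern holds as a minor internal inconsistency. As written, Section 15.13 sets two incompatible room-temperature limits, 46 h and 6 h, and the 46-hour figure is the likely error.

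That the sentences conflict follows directly from the text. Which figure is wrong is an inference, held with medium confidence. It rests on two assumptions: that the source page really shows 46, and that the Pharmacy Manual does not support it. Until this is confirmed, 6 hours is the safe working limit. The trial's endpoints, sample size, stopping rules and analyses are untouched.

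**What to change.** 1. Look at the source page of Section 15.13 for a struck-through digit, and compare the limit with the Pharmacy Manual.
2. If the page shows 46 and the manual confirms 6, change 46 to 6 in the storage sentence. Keep the word *cumulative* and the following sentence that counts bag storage and infusion time, so that the storage sentence and the discard rule state one limit with one way of counting it.
3. If the manual gives some other limit, put that value in both sentences.

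The cost is one figure in one sentence, plus the two checks. The only operational consequence is a shorter permitted holding time at room temperature; storage for up to 96 hours under refrigeration does not change.

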15.19 Nursing guidelines

15.191 Pembrolizumab side effects vary greatly from those of traditional chemotherapy and can vary in severity from mild to life threatening. Instruct patients to report any side effects to the study team immediately. Side effects may be immediate or delayed up to months after discontinuation of therapy. Most side effects are reversible with prompt intervention of corticosteroids.

15.192 Diarrhea can be seen however is less common than that seen with anti-CTLA-4 agents. However it can be severe, leading to colonic perforation. Instruct patients to report ANY increase in the number of stools and/or change in baseline, blood in the stool, abdominal pain to the study team immediately.

15.193 Rash/pruritus/dermatitis is seen. Patients should report any rash to the study team. Treat per section 9.0 and monitor for effectiveness.

15.194 Monitor LFT's closely as elevations in these levels could indicate early onset autoimmune hepatitis. Patients should also be instructed to report any jaundice, or right upper quadrant pain to the study team immediately.

15.195 Pneumonitis can be seen and may be mild (only seen on imaging) to severe. Patients should be instructed to report any SOB, dyspnea, cough, chest pain, etc. to the study team immediately. Patients reporting these symptoms should have a pulse ox checked and consider immediate imaging per the treating MD.

15.196 Endocrinopathies (including hypopituitarism, hypothyroidism, hypophysitis, and adrenal insufficiency) are seen with this agent. Patients may present only with the vague sense of fatigue and "not feeling well". Additional symptoms may be that of nausea, sweating and decreased activity tolerance. Instruct patients to report these signs or symptoms immediately and obtain appropriate labs as ordered by MD.

15.197 Patients who are started on steroid therapy for any side effects of pembrolizimab toxicity should be instructed to take the steroids as ordered, and not to discontinue abruptly as symptoms may return and be severe. Patients may be on steroid therapy for weeks. Instruct patients to report any increase or change in side effects with any dosage decrease as patients may need a slower taper.

15.198 Fatigue is common and may or may not be associated with immune related side effects. Assess patient's fatigue level prior to each cycle of therapy and report any changes to the study team.

15.199a Patients should avoid receiving live vaccines within 30 days of study drug administration or per other study guidelines.

15.199b Patients who have undergone an allogenic bone marrow transplant, have an increased risk of severe complications including early GVHD, and venoocclusive disease, if they have previously been treated with pembrolizumab

15.199c Myocarditis has been reported and associated with pembrolizumab. Instruct patients to report chest pain, SOB, or dyspnea to study team immediately and/or seek emergency medical attention.

15.199d Autoimmune hematologic disorders including ITP and hemolytic anemia have been reported. Monitor blood counts closely and report any abnormalities to the study team.

15.199e Rare neurologic disorders including Guillain-Barre syndrome and myasthenia gravis have been reported. Instruct patients to report any neurologic symptoms including weakness, parasthesias or numbness, tingling to the study team immediately.

16.0 Statistical Considerations and Methodology

16.1 Overview

This is a phase II study designed to assess the overall cutaneous response rate at cycle 9 in MF patients treated with pembrolizumab. It is a single one-stage design with an interim analysis based on the Simon optimal design with 85% power and 10% Type I error.

NOTE: As per Amendment 4, accrual will cease after the enrollment of 10 patients due to sponsor decision on funding. Thus, the study power and type I error will not be appropriate for the analysis, as the study will not be able to go to full accrual. The study will be analyzed at the pre-defined interim step.

16.11 Endpoint:

The primary endpoint is overall cutaneous response (cutaneous complete response (CR), cutaneous 90 response (CR90) or cutaneous partial response (PR)) as defined using the mSWAT score as stated in section 11.0. Throughout Section 16.0, CR, CR90 or PR will be considered synonymous with “success”, unless specified otherwise. All patients meeting the eligibility criteria who have signed a consent form and have begun treatment will be evaluable for response.

16.2 Statistical Design

- 16.21 Design: The largest success proportion where the proposed treatment regimen would be considered ineffective in this population is 15%, and the smallest success proportion that would warrant subsequent studies with the proposed regimen in this patient population is 35%. This design uses 28 evaluable patients to test the null hypothesis that the true complete response rate is at most 15%.
- 16.22 Interim Analysis: Enter 10 evaluable patients to the study. If there are less than 2 successes in the first 10 evaluable patients, we will consider this regimen ineffective in this patient population and terminate this study. Otherwise, if the number of successes is at least 2, we will continue accrual.
- 16.23 **N/A as per Amendment 4:** Final Decision rule: If 6 or fewer successes are observed in the first 28 evaluable patients, we will consider this regimen ineffective in this patient population. Otherwise, if the number of successes is at least 7, this will be considered evidence of promising activity and the treatment may be recommended for further testing in subsequent studies.
- 16.24 **N/A as per Amendment 4:** NOTE: We will not suspend accrual at the interim analysis to allow the first 10 patients to become evaluable, unless undue toxicity is observed. Given the limited overall sample size and the inclusion of an adverse events stopping rule, we feel it is ethical to not halt accrual for the interim analysis. However, if accrual is extremely rapid, we may temporarily suspend accrual in order to obtain safety data on these patients before re-opening accrual to further patients.

